Study Drug Accountability				X		X	X	X	X		
Blood Collection for Biomarker											
Banking							X		X		
Craft Story 21 Recall	X						X		X		
Letter & Category Fluency	X						X		X		
Number Span Test	X						X		X		
MoCA	X						X		X		

^{1.} Baseline visit for the Extension Phase is only required if there is an extended break (≥4 weeks) in dosing between the Randomization and Extension Phases.

^{2.} For participants who will have been off of the study drug for less than or equal to 4 weeks, the subject should come into the investigative site for an Abbreviated Drug Dispensation Visit (also "Abbreviated OLE Baseline Visit"), at which time any major medical or medications changes will be reviewed prior to dispensing riluzole. In this case, most procedures from the Week 48 visit will also serve as the Open-Label Extension Phase Baseline visit

Protocol BHV4157-203

- 3. Extension Week 8 is primarily to collect Liver Function tests. If a participant prefers not to come into the office, these can be collected at a local laboratory, with a telephone call confirming these were collected as well as a review of concomitant medications and an assessment of any adverse events. If the participant comes into the center, an assessment of adverse events and Liver function tests will be completed. Although all other visits can be conducted remotely as needed due to COVID-19 restrictions, under regular circumstances visits are to be completed in-person. See Protocol Section 8.1.12, Open-Label Extension Phase, for further details and requirements regarding remote visit completion due to COVID-19.
- 4. The following must be collected at any unscheduled visit: vital signs, prior and concomitant medications, adverse events, and protocol deviations. All other unscheduled visit procedures are subject to PI discretion or request from the Medical Monitor.
- 5. Telephone calls to subjects will be made between visits during Extension Phase (Weeks 2 and 8) to monitor subject condition, review concomitant medications and assess any adverse events.

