#### 4.8.5.2 Composite Neuropsychological Test Battery Score

A cognitive composite outcome measure will be computed using measures from the NACC Neuropsychological Test Battery. The composite outcome will comprise the overall average of the Z-scores from each of the following NACC subtest measures: Craft Story 21 total immediate Recall; Craft Story 21 total delayed recall; Benson Figure copy score; Benson Figure delayed recall; Multilingual Naming Test total correct; Letter Fluency total score; Category Fluency total score; Trail Making Test A time to completion; Trail Making Test B time to completion; Number Span Forward total correct; and Number Span Backward total correct. Z-scores for each participant on each measure will be calculated using the overall average of all participants at baseline as reference.

The total composite neuropsychological test battery score will be calculated as the overall average Z-score from each of the completed subtests. If more than 2 NACC Neuropsychological Test Battery subtest measures are missing, the total composite neuropsychological test battery score will be missing. Please refer to Appendix 3 regarding prorating subtest scores when there are partially (i.e., item-level) missing data.

The change from baseline in composite neuropsychological test battery score will be analyzed using the mITT set via a mixed model as above. However since there are no repeated measures on participants, there will not be a participant-level random effect. This analysis is exploratory for potential publication purposes only.

In addition, descriptive statistics will also be presented by visit in the Open Label Extension Phase, by original randomized group (BHV-4157 and Placebo to BHV4157).

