# Table 2: Schedule of Assessments and Events – Open-Label Extension Phase

Visit Number	1	2	3	4	5	6	7	8	9	10	
Study Visit Timepoint	Baseline 	Abbrev- iated Drug Dispensat ion Visit 	Ext Week 2 (+/- 7 days)	Ext Week 4 (+/- 7 days)	Ext Week 8  (+/- 7 days)	Ext Week 12 (+/- 7 days)	Ext Week 24 (+/- 7 days)	Ext Week 36 (+/- 7 days)	Ext Week 48 or Early Term (+/- 7 days)	Week2 Post last dose (+/- 7 days)	Unsched- uled Visit  (+/- 7 days)
Informed Consent	Х	Х									
Medical History	Х										
Adverse Event Assessment	Х	Х	Х	Х	X 	Х	Х	Х	Х	Х	
Telephone Check-in  Includes AE assessment and concomitant medication review			Х		X 						
Laboratory Assessments 	Х			Х	X 	Х	Х	Х	Х		
Urinalysis	Х						Х		Х		
Physical Exam	Х								Х		
Physical Measurement - Weight	Х						Х		Х		
Vital Signs	Х	Х		Х		Х	Х	Х	Х	Х	Х
12-Lead ECG	Х					Х	Х		Х		
Concomitant Medication Review	Х	Х	Х	Х	Х	Х	Х	Х	Х	Х	Х
Sheehan Suicidality Tracking Scale (S-STS)	Х	Х		Х		Х	Х	Х	Х	Х	
Dispense Study Drug	Х	Х		Х		Х	Х	Х			
Volumetric MRI 	Х								Х		
ADAS-Cog 11	Х						Х		Х		
CDR-SOB	Х						Х		Х		
Study Drug Accountability				Х		Х	Х	Х	Х		
Blood Collection for Biomarker											
Banking							Х		Х		
Craft Story 21 Recall	Х						Х		Х		
Letter & Category Fluency	Х						Х		Х		
Number Span Test	Х						Х		Х		
MoCA	X						X		X		

ADCS & Biohaven Pharmaceuticals Protocol BHV4157-203 Confidential 03DEC2020

- 1. Baseline visit for the Extension Phase is only required if there is an extended break (≥4 weeks) in dosing between the Randomization and Extension Phases.
- 2. For participants who will have been off of the study drug for less than or equal to 4 weeks, the subject should come into the investigative site for an Abbreviated Drug Dispensation Visit (also "Abbreviated OLE Baseline Visit"), at which time any major medical or medications changes will be reviewed prior to dispensing riluzole. In this case, most procedures from the Week 48 visit will also serve as the Open-Label Extension Phase Baseline visit

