# APPENDIX 3 - Calculating the composite neuropsychological test battery score when there are missing data

A cognitive composite outcome measure will be computed using measures from the NACC Neuropsychological Test Battery. The composite outcome will comprise the overall average of the Z-scores from each of the following NACC subtest measures: Craft Story 21 total immediate Recall; Craft Story 21 total delayed recall; Benson Figure copy score; Benson Figure delayed recall; Multilingual Naming Test total correct; Letter Fluency total score; Category Fluency total score; Trail Making Test A time to completion; Trail Making Test B time to completion; Number Span Forward total correct; and Number Span Backward total correct. Z-scores for each participant on each measure will be calculated using the overall average of all participants at baseline as reference.

Missing total scores for subtest measures from the NACC Neuropsychological Test Battery are designated as missing for the following reasons:

- Participant Unable for Cognitive Reasons
- • Participant Unable for Other Reasons (Physical, auditory, etc.)
- · Participant/Study Partner Refused
- · Oversight
- · Other Reason
- · Unknown

When total scores for subtest measures are missing because the participant was unable to complete the task for cognitive reasons, the worst possible score for the measure will be assigned. Total scores that are missing for any other reason will be treated as missing in calculating the composite neuropsychological test battery score.

For partially missing (item-level) missing data, if fewer than 25% of items within a NACC subtest measure are missing, scores for the missing items will be prorated as the average of the completed items on that subtest. This procedure will be employed for a maximum of two NACC subtests. If more than 25% of the items within any NACC subtest are missing, the entire subtest is missing.

The total composite neuropsychological test battery score will be calculated as the overall average Z-score from each of the completed subtests. If more than 2 NACC subtests are missing, the total composite neuropsychological test battery score will be missing.

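### The extension collects only 6 of the 11 measures in the neuropsychological composite, so under the SAP's own missing-data rule no composite score can exist after extension baseline

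*SAP*

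**What the plan says.** SAP 4.8.5.2 defines the composite as a mean of Z-scores. The list opens with four scores from two memory and drawing tasks: "Craft Story 21 total immediate Recall; Craft Story 21 total delayed recall; Benson Figure copy score; Benson Figure delayed recall". Four more follow, covering naming, fluency and the first Trails task: "Multilingual Naming Test total correct; Letter Fluency total score; Category Fluency total score; Trail Making Test A time to completion". Three scores close the list: "Trail Making Test B time to completion; Number Span Forward total correct; and Number Span Backward total correct". That makes 4 + 4 + 3 = 11 in all. Each is standardised against all participants at baseline.

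The section then limits missing data: "If more than 2 NACC Neuropsychological Test Battery subtest measures are missing, the total composite neuropsychological test battery score will be missing". SAP Appendix 3 repeats the limit: "If more than 2 NACC subtests are missing, the total composite neuropsychological test battery score will be missing". Under Appendix 3, the worst possible score replaces a missing subtest only when the participant could not do the task for cognitive reasons. A total missing for any other reason stays missing. Proration applies to items within a partly completed subtest.

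The section ends with a commitment for the extension: "In addition, descriptive statistics will also be presented by visit in the Open Label Extension Phase, by original randomized group".

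The extension schedule is in Protocol Appendix I, Table 3, and in SAP Appendix 1, Table 2 (printed twice, with the same test rows). It has three rows from this battery: Craft Story 21 Recall, "Letter & Category Fluency" and "Number Span Test". Each is marked at extension Baseline, Week 24 and Week 48. The double-blind schedule (Table 1 in both documents) has six rows from the battery, marked at Baseline and Week 48.

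**The concern.** The scoring rule was written for a visit at which the whole battery is given. The extension gives a shortened battery, and the SAP neither defines a shortened composite nor exempts the extension from the limit. Followed literally, the plan promises by-visit statistics on a score that cannot exist at the scheduled extension visits after baseline.

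Two things are at stake, both modest. First, participants sit six measures at each of these visits, and the planned composite summary uses none of them. Second, the gap invites an improvised substitute. SAP 4.5.2 places the unblinded double-blind analysis before the final extension analysis, so a substitute chosen late could be chosen by people who have seen results by arm. If that substitute averaged the six available measures and compared them with an 11-measure baseline, the change would partly reflect the removal of naming, figure copying and recall, and Trails.

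**Working it through.** The plan states no figure to reproduce here. The check is a count of measures against the two schedules.

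**Inputs.** The 11 measures come from SAP 4.8.5.2. The tests given come from Tables 1 and 3 of Protocol Appendix I and Tables 1 and 2 of SAP Appendix 1. The limit of 2 comes from SAP 4.8.5.2 and Appendix 3.

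| Test (schedule row) | Measures in composite | Double-blind Baseline, Week 48 | Extension visits |
|---|---|---|---|
| Craft Story (immediate, delayed) | 2 | 2 | 2 |
| Benson Figure (copy, delayed) | 2 | 2 | 0 |
| Multilingual Naming Test | 1 | 1 | 0 |
| Letter and Category Fluency | 2 | 2 | 2 |
| Trail Making A and B | 2 | 2 | 0 |
| Number Span (forward, backward) | 2 | 2 | 2 |
| **Total** | **11** | **11** | **6** |

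**Rule.** The composite is missing if (11 − measures given) > 2, so at least 11 − 2 = 9 measures are needed.

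- Double-blind Baseline and Week 48: 11 − 11 = 0 missing by design; the score can be computed.
- Extension visits: 11 − 6 = 5 missing by design; 5 > 2, so the score is missing. Even a participant who completes everything offered is 9 − 6 = 3 measures short.

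**Counting by test instead of by measure.** The extension gives 3 of 6 tests, so 6 − 3 = 3 are missing; 3 > 2, and the result is the same.

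**Do other rules rescue the score?** Item-level proration needs a partly completed subtest, and these subtests are not given at all. Worst-score assignment needs cognitive inability, which is not the reason here. The instruction to average completed subtests is itself subject to the limit.

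**Extension baseline.** Protocol sections 2 and 8.1.12 distinguish two situations.

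- For direct rollovers, the double-blind Week 48 visit is the extension baseline. For those off drug for 4 weeks or less, most Week 48 procedures serve that purpose. That visit includes the full battery, so an 11-measure baseline score can exist, subject to the 28-day limit under Table 4 of SAP 4.3.8.
- Participants off drug for longer repeat the baseline visit with the 6-measure battery. Their composite is missing at that visit too.

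**Change.** SAP 4.5.2 measures extension change from the extension baseline unless otherwise specified. The post-baseline term is missing for everyone, so no change can be computed, whichever baseline applies.

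**The case against.** The strongest counter-argument is about weight. SAP 4.8.5.2 describes the composite's model as exploratory and for possible publication only. Protocol 12.7 and 12.7.1 make extension efficacy exploratory and descriptive. No test, alpha allocation, estimand or analysis population depends on this summary. All of that stands and limits the point.

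A reader might infer that the whole extension table would be empty. The documents do not support that: an 11-measure baseline row can exist for participants whose double-blind Week 48 visit serves as extension baseline. What is lost is every score after baseline.

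A reader might also infer that the extension's long-term clinical objective fails. It does not. That objective (Protocol 4.3.1; SAP 1.2.3 and 2.4.3) is general and does not name the composite. ADAS-Cog 11, CDR-SOB and MoCA are all scheduled at extension Weeks 24 and 48. Nor do the documents suggest that analysts will disregard the limit and average six measures; that harm is conditional.

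Two textual objections are weaker. The extension sentence does not name its variable, but it closes a section about this composite alone, and similar sentences close SAP 4.8.3 and 4.8.4.1 for their own endpoints. And Appendix 3's list of reasons for missing subtests has no entry for a test that was not scheduled, which suggests that the authors had the full battery in mind. However, the list includes an open category, and the text treats every non-cognitive reason as missing. This explains how the gap arose without closing it.

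**Conclusion.** The inconsistency is real and follows from the documents alone. Under the SAP as written, 100% of composite scores at extension Weeks 24 and 48 are missing (5 of 11 measures absent, limit 2), as is any repeated extension baseline after a long dosing break. Baseline scores taken from the double-blind Week 48 visit can survive, but they have nothing to be compared with.

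This rests on three assumptions: that the closing sentence of SAP 4.8.5.2 refers to the composite, that the missing-data limit applies in the extension because no exemption is given, and that sites do not administer the omitted tests outside the schedule.

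The consequence is limited to one exploratory, descriptive summary. The co-primary, secondary and double-blind composite analyses are unaffected. It should still be corrected, because a planned output is defeated by its own scoring rule and the correction is cheap.

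**What to change.** In SAP 4.8.5.2 and Appendix 3, define an extension composite from the six measures collected: Craft immediate and delayed recall, Letter Fluency, Category Fluency, and Number Span forward and backward. Standardise it to the double-blind baseline, as for the full composite. Recompute double-blind Baseline and Week 48 on the same six measures so that change is like-for-like. Scale the missing-data limit; keeping the present proportion gives 6 × 2/11 = 1.09, that is, at most one missing measure. Keep the 11-measure composite for the double-blind phase.

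Two lighter edits also remove the contradiction: summarise the six measures individually in the extension, or delete the extension composite summary. Whichever is chosen should be written down before the double-blind results are unblinded.

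The cost is a few lines of SAP text and, for the first two options, some programming. No new data are needed, because all six measures are scheduled at double-blind Baseline and Week 48. The downside is that an extension summary based on these six measures does not cover naming, visuospatial or Trails performance, which the extension does not collect.

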#### 4.8.5.3 ADCOMS

The AD Composite Score (ADCOMS) is a weighted composite outcome optimized for progression in an MCI stage of AD, and comprised of scores from 4 ADAS-Cog subscales (Delayed Word Recall, Orientation, Word Recognition, and Word Finding Difficulty), 2 MMSE items (Orientation to Time, and Intersecting Pentagons), and the CDR Sum of Boxes (Wang et al., 2016). Because Delayed Word Recall is not assessed within this trial, the ADCOMS cannot be calculated using the methods and weights described by Wang and colleagues (2016) and this

composite is not optimized for the mild-to-moderate population included in our study. However, exploratory analyses may be run using historical data from a similar mild-to-moderate population to combine and weight elements of the ADAS-Cog and MMSE with the CDR-SB to develop a composite score using similar methodology. Change from baseline to Week 48 on this composite outcome will be analyzed using the mITT set via an MMRM analysis model to assess impact on AD progression.

#### 4.8.5.4 CSF, Serum and Plasma Biomarker Panel

CSF, serum and plasma biomarker panel (including, for example, AB42, AB42/40 ratio, total tau, p-tau-181, neurogranin, NfL, YKL-40, VILIP, SNAP-25, sTREM2, GFAP) will be assessed at screening, week 24 and week 48. CSF will be collected and analyzed in a subset of the study population (estimated n=50 active, n=50 placebo) at screening, week 24 and week 48.

The change from baseline in the response through week 48 will be analyzed using the mITT population via a Mixed Model for Repeated Measures (MMRM) analysis model, similar to the primary analysis. Fixed effects in the models are APOE status (e4 carrier vs e4 noncarrier), baseline score, treatment group (active vs placebo), visit, visit x baseline score, and visit x treatment group interaction. If appropriate, the response variable will be log transformed. Subjects who have a baseline measure and at least one evaluation on-treatment following baseline will form the study population for this analysis.

Summary statistics will be provided by arm. A p-value and 95% confidence interval for the estimated effect will be included in the summary.

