8.1.1 Screening (within 42 days prior to baseline)

Participants whom the Investigator considers to be appropriate for the study, will have the study explained to them, their LAR if applicable, and their study partner by the Investigator or his/her designee and will be given a copy of the written Informed Consent Form (ICF). When they have had sufficient time to study this information and the opportunity to ask any questions they wish, they will be invited to give their consent to participation by signing the ICF. The study partner

may also be required to sign the ICF at the discretion of the responsible IRB reviewing this research. Participants who are willing to participate in the CSF sub-study will so indicate in the section provided on the ICF.

Once the participant or LAR (and study partner if required) have given consent, the following procedures will be undertaken during the screening period.

- Confirmation of probable Alzheimer's disease using the NIA/Alzheimer's Association Guidelines (see Appendix II)
- MMSE (score between 14 to 24, inclusive)
- Documentation of demographics, medical history, smoking habits and education
- Modified Hachinski ischemic test (score of 4 or less)
- Neurological exam
- Physical examination
- Vital signs (sitting blood pressure, pulse, temperature, respiration rate)
- Weight
- Height
- Documentation of concurrent pathologies and concomitant treatment
- Documentation of adverse events from time of consent. Adverse events that occur prior to initiation of study drug will be documented as medical history.
- Blood samples for:
 - Clinical safety laboratory tests (hematology and serum chemistry, as listed in Section 8.2).
 - HIV, HBsAg, HCV antibody
 - ApoE (e4 +/-) genotyping
- Urinalysis (see Section 8.2)
- Resting 12-lead ECG
- Volumetric MRI per protocol imaging requirements;
 - o If a participant has not had an MRI performed within 6 months of screening (i.e., within 6 months from the date of informed consent), then an MRI must be performed as part of the screening requirements for this study, per the imaging protocol, and should be one of the last screening procedures performed to determine final eligibility in order to prevent participants from undergoing unnecessary MRIs.

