 - Week 24 and week 48 vMRI: the protocol window for vMRI at week 24 and week 48 is 14 days before and up to 14 days after the clinic visit. If participant is terminating early at 36 week or after, obtain vMRI if MRI is performed on the same day as a lumbar puncture at week 48, the vMRI must be conducted before the lumbar puncture. Otherwise, at least a 3-day window between vMRI and the lumbar puncture is required.
- 12 It is anticipated that lumbar puncture will be performed on an estimated 100 study participants as part of a sub-study (separate informed consent required).
- Only for the CSF sub-study. Visit windows for CSF are: up to 14 days prior to first dose of study medication and up to 14 days prior to weeks 24 and 48. If a participant in the CSF sub-study is terminating early, they do not need to undergo lumbar puncture.
- Post lumbar puncture safety follow up telephone call must occur 1 to 3 days after the lumbar puncture is performed.
- First dose of study medication will be given in the clinic at the baseline clinic visit after completion of the baseline visit procedures.
- Participants will receive a phone call during Week 2 from site study personnel in order to assess study drug tolerability. If tolerable, then the participant will be instructed to proceed with dose escalation.
- 17 Treatment blinding questionnaire to be administered to site PI and Raters.

Table 3: Schedule of Assessments and Events – Open-Label Extension Phase

Visit Number	1	2	3	4	5	6	7	8	9	10	
Study Visit Timepoint	Baselinel	Abbrev- iated Drug Dispensat ion Visit ²	Ext Week 2 (+/- 7 days)	Ext Week 4 (+/- 7 days)	Ext Week 8 ³ (+/- 7 days)	Ext Week 12 (+/- 7 days)	Ext Week 24 (+/- 7 days)	Ext Week 36 (+/- 7 days)	Ext Week 48 or Early Term (+/- 7 days)	Week2 Post last dose (+/- 7 days)	Unsched- uled Visit ⁴ (+/- 7 days)
Informed Consent	X	X									
Medical History	X										
Adverse Event Assessment	X	X	X	X	X^3	X	X	X	X	X	X
Telephone Check-in ⁵ Includes AE assessment and concomitant medication review			X		X ³						
Laboratory Assessments ⁶	X			X	X^3	X	X	X	X		
Urinalysis	X						X		X		
Physical Exam	X								X		
Physical Measurement - Weight	X						X		X		
Vital Signs	X	X		X		X	X	X	X	X	X
12-Lead ECG	X					X	X		X		
Concomitant Medication Review	X	X	X	X	X	X	X	X	X	X	X
Sheehan Suicidality Tracking Scale (S-STS)	X	X		X		X	X	X	X	X	
Dispense Study Drug	X	X		X		X	X	X			
Volumetric MRI ⁷	X								X		
ADAS-Cog 11	X						X		X		
CDR-SOB	X						X		X		

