#### 4.3.3 Adjustments for Covariates and Stratification

The analysis of the primary endpoints and other efficacy endpoints will be analyzed by comparing the change in efficacy outcome at week 48 between treatment groups using a mixed model with repeated measures (MMRM). Fixed effects in the model are APOE status (e4 carrier vs e4 noncarrier), MMSE (mild vs moderate) status, site, baseline value of the endpoint, treatment group (active vs. placebo), visit, visit x baseline and visit x treatment group interaction. Visit is treated as a categorical variable (see section 4.2.8 for definition of visit windows to be use). Subject will be included as random effects in the model. Sites with only one subject will be pooled together.

A stratified permuted block randomization procedure will be used. The stratification factors will be Screening Visit MMSE [mild: 20 to 24; moderate: 14 to 19] and Site.

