#### 4.8.3 Analysis of the Co-Primary Outcome Measures

The primary analyses use the within-participant change in ADAS-Cog 11 and in CDR-SOB as the outcome in two separate similar mixed effects repeated measures models, including all available in-clinic outcomes during the double blind phase in the mITT population. Fixed effects in the models are APOE status (e4 carrier vs e4 noncarrier), MMSE (mild vs. moderate) status, site, baseline ADAS-Cog or CDR-SOB score, respectively, treatment group (active vs placebo), visit, visit x baseline score interaction, and visit x treatment group interaction. Visit is treated as a categorical variable. Sites with only one subject will be pooled together. Descriptive statistics showing the timing of the primary outcome assessment will be presented by treatment arm as well as break-outs by baseline characteristics (e.g. APOE status, Mild/Moderate status based on MMSE, age group, and sex).

A random effect will be included for participant. The within-participant covariance will be unstructured. If the model does not converge, MMSE status will be removed from the model. If the model still does not converge, the following structures for the within-subject covariance will be fit, sequentially, until the structure is found that results in convergence of the model: Huynh-Feldt, Toeplitz, Autoregressive (1), and Compound Symmetry. Error degrees of freedom will be calculated using the Kenward-Roger approximation if an unstructured covariance is used; otherwise, a sandwich estimator will be utilized to estimate the covariance structure and degrees of freedom will be calculated using the between-within method. For the ADAS-Cog 11and CDR-SOB, each primary endpoint will be tested using model-adjusted least squares means at the week 48 visit. Point estimates, standard errors, two-sided 95% confidence intervals, and p-values will be presented.

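### The biomarker MMRM leaves out MMSE status, a two-level randomisation stratum that the SAP's general covariate rule includes; restoring it costs almost nothing and may gain a little precision

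*SAP*

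**What the plan says.** SAP 4.8.5.4 analyses change in the CSF, serum and plasma markers "via a Mixed Model for Repeated Measures (MMRM) analysis model, similar to the primary analysis". It then lists the terms: "Fixed effects in the models are APOE status (e4 carrier vs e4 noncarrier), baseline score, treatment group (active vs placebo), visit", with visit-by-baseline and visit-by-treatment interactions. Neither MMSE status nor site appears.

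Three other parts of the SAP bear on this.

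- Section 4.3.3 sets a general rule. It opens "The analysis of the primary endpoints and other efficacy endpoints will be analyzed by comparing the change in efficacy outcome at week 48" and lists APOE status, MMSE status, site, baseline, treatment, visit and the same two interactions. The biomarker panel falls under 4.8.5, which is headed as exploratory efficacy endpoints. The same section says of the randomisation: "The stratification factors will be Screening Visit MMSE [mild: 20 to 24; moderate: 14 to 19] and Site".
- Section 4.8.3, the co-primary model, reads "Fixed effects in the models are APOE status (e4 carrier vs e4 noncarrier), MMSE (mild vs. moderate) status, site" and continues with the remaining terms. MMSE status is removed only if the model fails to converge.
- Section 4.8.4.1, volumetric MRI, also uses a shortened model. It leaves out site and APOE but keeps baseline MMSE.

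CSF comes from a voluntary subset, estimated at 50 per arm. Protocol 8.1.1 records willingness at screening: "Participants who are willing to participate in the CSF sub-study will so indicate in the section provided on the ICF". Blood for biomarkers is scheduled at the main visits (Protocol Appendix I, Table 1), although Protocol 8.8 also speaks of consenting participants for it.

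**The concern.** The biomarker model keeps APOE, a two-level factor that was not used in randomisation, and drops MMSE status, a two-level factor that was. A small sample can justify leaving out site, which may use many degrees of freedom. It cannot justify leaving out a single two-level term while another is kept. The general and specific sections therefore disagree, and no reason is given.

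At stake is the precision of the biomarker contrasts, for which 4.8.5.4 promises p-values and 95% confidence intervals. If severity predicts biomarker change, leaving it out puts explainable variation into the error term. In the CSF subset the permuted blocks are no longer intact, so the arms may also differ by chance in their mix of mild and moderate disease, with nothing in the model to correct for it except baseline biomarker value and APOE.

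**Working it through.** The plan states no power or precision for biomarkers; its power figures concern only the co-primary endpoints. There is no plan figure to reproduce here.

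**Inputs from the documents.** MMSE status has 2 levels. CSF subset: 50 + 50 = 100. Assumed dropout: 26% (SAP 4.2), so 100 × 0.74 = 74. Test: two-sided 0.05.

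**Assumptions, not in the documents.** The difference in mean biomarker change between MMSE strata, g, runs from 0 to 0.8 residual SD. The stratum share, q, runs from 30% to 70%. The illustrative treatment effect is 0.5 SD.

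**1. Cost of the term.** Take a one-visit (week 48) version of the model with intercept, treatment, APOE and baseline, which is 4 parameters.

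- n = 100: residual df go from 100 − 4 = 96 to 95; the critical t goes from 1.9850 to 1.9853 (+0.013%).
- n = 74: residual df go from 70 to 69; the critical t goes from 1.9944 to 1.9949 (+0.025%).

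**2. Residual SD when the term is omitted.** The inflation factor is √(1 + g²·q(1 − q)). With q = 0.5:

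- g = 0: 1.000
- g = 0.3: √1.0225 = 1.011
- g = 0.5: √1.0625 = 1.031
- g = 0.8: √1.16 = 1.077

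**3. Chance imbalance in the CSF subset.** The worst case is that no stratification benefit carries over. The SD of the arm difference in stratum share is √(2q(1 − q)/50), which is 0.10 at q = 0.5 and 0.092 at q = 0.3 or 0.7. By simulation, the chance of a difference of at least 10 percentage points is 33% to 37%, and of at least 20 points 4% to 6%. The shift in the estimate is imbalance × g. At g = 0.5 that is 0.10 × 0.5 = 0.05 SD for 10 points and 0.10 SD for 20 points. For scale, the standard error of the contrast with 50 per arm is about √(2/50) = 0.20 SD, so a 10-point imbalance moves the estimate by about a quarter of one standard error.

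**4. Error rate, power and interval width.** ANCOVA simulation with n = 100, q = 0.5, an adjusted baseline covariate unrelated to the stratum, and 8,000 runs per cell. *Balanced* means that allocation is balanced by stratum within the subset; *free* means that it is not. Each cell gives the result without / with the MMSE term.

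| g (SD) | Type I, balanced | Type I, free | Power, balanced | Power, free | 95% CI width, balanced | 95% CI width, free |
|---|---|---|---|---|---|---|
| 0 | 0.050 / 0.050 | 0.052 / 0.051 | 0.687 / 0.686 | 0.689 / 0.683 | 0.797 / 0.797 | 0.796 / 0.800 |
| 0.3 | 0.048 / 0.049 | 0.049 / 0.048 | 0.678 / 0.686 | 0.679 / 0.683 | 0.805 / 0.796 | 0.806 / 0.802 |
| 0.5 | 0.046 / 0.052 | 0.052 / 0.049 | 0.669 / 0.691 | 0.672 / 0.695 | 0.820 / 0.795 | 0.821 / 0.801 |
| 0.8 | 0.033 / 0.049 | 0.049 / 0.051 | 0.640 / 0.692 | 0.626 / 0.687 | 0.857 / 0.796 | 0.857 / 0.800 |

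The Monte Carlo standard error near 0.05 is √(0.05 × 0.95/8000) = 0.0024, so nothing here shows inflation. With balance kept, omission makes the test conservative, clearly so only at g = 0.8. With free allocation the test without the term holds its level, but it carries avoidable noise. The worst case for adding the term is g = 0 under free allocation, where the interval widens from 0.796 to 0.800, about 0.5%.

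**The case against.** The strongest defence is that 4.8.5.4 is a specific list, that it claims only similarity to the primary analysis, and that the SAP tailors covariates elsewhere, as in the MRI model. A specific section usually overrides a general one. The model already adjusts for baseline biomarker value, its interaction with visit, and APOE, and baseline may absorb much of any severity effect. The endpoints are exploratory, unadjusted for multiplicity and descriptive (SAP 4.3.4), so no trial decision rests on them. All of this stands and keeps the severity low. It does not supply a reason for the omission, and the other tailored model, MRI, kept MMSE.

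A reader might infer more than the documents support.

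- *That opting in to CSF biases the comparison.* Willingness is recorded on the consent form at screening and the first lumbar puncture precedes study drug, while randomisation is at the baseline visit (Protocol 8.1.1, 8.1.2, 8.8). The choice cannot depend on arm. A severity difference arising from it is chance imbalance, which the standard error already reflects on average. The requirement of at least one on-treatment evaluation is a selection after randomisation, but it is a separate matter, and an MMSE term is not aimed at it.
- *That false positives increase.* The simulation shows none.
- *That overstated standard errors and unadjusted imbalance apply together.* They need opposite conditions. The first requires balance to be kept, most plausibly in serum and plasma if most participants contribute; the second requires it to be lost, most plausibly in CSF.
- *That site must be restored too.* With about 100 CSF participants, leaving site out is defensible.

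**Conclusion.** The point holds as a low-severity, nearly free improvement. The 4.8.5.4 model omits a two-level randomisation stratum that 4.3.3 and 4.8.3 include, without a stated reason. The consequence is some loss of precision in exploratory analyses, not bias and not an inflated error rate.

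The possible gain runs from nil to modest. Over the assumed range of 0 to 0.8 SD between strata, omission inflates the residual SD by 0% to 7.7%. At 0.3 SD the effect on power is negligible. At 0.5 SD, power for a 0.5 SD treatment effect is about 0.67 without the term and 0.69 to 0.70 with it. At 0.8 SD it is 0.63 to 0.64 against 0.69. These figures rest on an MMSE–biomarker association that the documents do not give, a single-visit approximation to the MMRM, 100 analysed participants, and a baseline value that absorbs none of the severity effect. Relaxing the last assumption would shrink the gain.

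**What to change.** In SAP 4.8.5.4, add the screening MMSE stratum (mild 20 to 24, moderate 14 to 19) to the fixed effects. If a marker's model does not converge, use the sequence already set out in 4.8.3, which removes MMSE status first.

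Align 4.8.5.4 with 4.3.3: say that the biomarker model follows the general rule except that site is left out because the CSF subset is small. If the sponsor prefers to leave MMSE status out, the section should give the reason.

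The cost is one term in the model statement and one degree of freedom, with no new data, since the stratum is already recorded for randomisation. If severity proves unrelated to a marker and the subset is unbalanced, intervals would be about 0.5% wider. The change should be made before unblinding.
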